All participants in this study will be de-identified.

Outcomes

Hospitalisation outcomes of interest will include the following conditions.

Mother	ICD-10-CM
Still birth, preterm birth pregnancy complications	P95 Stillbirth ⁹ O60 Preterm labour Z37 Outcome of delivery 
 • Single stillbirth • Twins, one liveborn and one stillborn • Twins, both stillborn • Other multiple births, all stillborn O00-O99.9 Pregnancy, childbirth and the puerperium
Infant	
Certain conditions originating in the perinatal period	Newborn affected by maternal factors and by complications of pregnancy, labour, and delivery P00-P96
Early neonatal death, SIDS	Ill-defined and unknown causes of mortality R95-R99.9
Congenital anomalies (CVS, CNS, other)	Congenital malformations, deformations and chromosomal abnormalities Q00-Q99.9
Infectious Diseases (pertussis, , etc.)	Certain infectious and parasitic diseases A00-B99
Meningitis	Meningitis due to other and unspecified causes G03 
 •arachnoiditis NOS •leptomeningitis NOS •meningitis NOS •pachymeningitis NOS
Encephalitis	Encephalitis, myelitis and encephalomyelitis G04 
 •acute ascending myelitis •meningoencephalitis •meningomyelitis
Lower respiratory (bronchiolitis, asthma, pneumonia, acute unspecified LRTI, bronchiectasis, Acute bronchitis, lung abscesses/pyothorax	Diseases of the respiratory system J00-J99
Neurological	Diseases of the nervous system G00-G99

⁹ Information about stillbirths is recorded in the Mortality Collection. The Mortality Collection includes extra information about fetal and infant deaths, such as gestation and birth weight. The ICD codes we propose are: P95 Fetal death of unspecified cause Z37 Outcome of delivery, Z37.1Single stillbirth, Z37.3 Twins, one live born one stillborn, Z37.4 Twins, both stillborn, Z37.7 Other multiple births, all stillborn

Pregnancy duration will be classified using the gestational age field from the National Maternity Collection data set. This field gives the duration of pregnancy in number of completed weeks. Preterm will be defined as birth before 37 weeks gestation. Normal term will be defined as birth between 37 and 41 weeks gestation. Post-term will be defined as birth after 41 weeks gestation.

The following codes are available so we can get banded weeks of gestation.

1518 Duration of pregnancy

Code	Number	
O09.0	<5	Completed weeks
O09.1	5-13	Completed weeks

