Vaccinee data verified as non-duplicated, then NHI number, name and phone number will be replaced by a sequential number (These are the only variables that contain personal identifiable information and will also be used to ensure there is no duplication of survey and extraction of maternal and pregnancy data at the end of the study).

Data set validation

Data set will be double entered for validation

Any corrections will be reviewed by a third party

Data confidentiality

No names or NHI numbers will be published

Visibility of the National Health Index number (NHI) of the participant's records will be password protected and restricted to the key investigators before being removed at the end of the study.

Access to complete data sets will be limited to the investigators and data analysts.

Data storage

The datasets will be stored in a password-protected file within The University of Auckland and the physical files will be held in a locked filing cabinet by the Principal Investigator/s [name] who will store it for 10 years in accordance with the NZ ethical guidelines.

Study duration

	Intensive study	Population datalink study
Month one	First participants enrolled in intensive study	
Month six	Last participants enrolled in intensive study (this potentially may be extended depending on enrolment)	Preparation for population data collection. Obtain ethical approval
Month 12	Interim report due	Receive 2009-2013 data, commence data cleansing and data matching
Month 18	Last of the 1 year follow up data will be collected	Commence analysis
Month 20	Final study report due	
Month 22	Submission of publication	
Month 24		Final report
Month 28		Submission of publication

Statistical analysis and sample size justification

Study One (N=~325,000)

Sample size:

Over the five-year period of this study there will be approximately 325,000 births. The percentage vaccinated will increase over the time period as the funded vaccine is promoted over the epidemic but on average approximately 30% of mothers would be expected to have received vaccination during pregnancy.

Analysis:

Logistic regression will be used to estimate odds ratios for the risk for (specific) adverse events for both mothers and infants in vaccine exposed and unexposed groups. Age, ethnicity and socioeconomic deprivation and season for hospital admission will be included as additional explanatory variables.

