As specific diagnoses are not necessarily independent events each person will only be counted once for each hospitalisation, the primary diagnosis and repeat admissions for the same episode will be removed, including transfers from one hospital to another.

For diagnosis where individuals may have multiple admissions for different occurrences and the outcome is a count, Poisson regression will be used with testing and adjustment for overdispersion where required.

The temporal relationship between onset of events and vaccination will be presented including distribution where appropriate,

Serious adverse events will be reported as detailed clinical cases.

To analyse the effect of Tdap on still births we will perform a survival analysis. The time dependent explanatory variable of vaccination status and 'failure' of still birth and censored at birth, also including demographics as explanatory variables. The independent explanatory variable will be Tdap vaccination status of the mother (time dependent). Time will commence at the beginning of the inclusion time for an individual— 28(20) weeks gestation. Women will be censored at time of live birth or at the end of the study period, 31 December 2013, whichever occurs first.

Study Two (N=~300)

Estimated number of women receiving pertussis vaccine during pregnancy for study period, potential study population

The birth cohort in NZ is approximately 65,000 per annum. Tdap is funded for pregnant women, but it is difficult to estimate how many women will take up the vaccine. In one DHB with a birth cohort of 6,000 who were first to offer pertussis vaccine free to pregnant women, 220 claims for the Tdap vaccine had been lodged in six weeks and 1,164 over eight months. At the 10th June 2012, out of 255 claims processed at that time 22 (9%) of women had not consented to follow up. The number of women able to be recruited to the Canterbury study is limited by available nurse time.

Based on the experience in Canterbury assuming sufficient workforce capacity the potential number of women available for follow up over a one-year period is:

National birth cohort 65,000

Uptake of pertussis vaccine in pregnancy 10–40%

Potential annual vaccinated cohort 6,500–26,000

Likely to consent (90%) 5,850–23,400

Eligible to participate (87%) 5,090–22,620

- Participation by general practices (success in obtaining informed consent to follow up) estimate 30–90% (likely to be higher rather than lower)

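### The Study One infant outcome Meningitis is defined only by G03, a residual code, so meningitis coded to a specified cause is not counted as Meningitis

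*Protocol*

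**What the plan says.** The Outcomes section for Study One opens its table with the statement "Hospitalisation outcomes of interest will include the following conditions". The infant part has eight rows, three of which bear directly on this point:

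- **Meningitis:** one code, "Meningitis due to other and unspecified causes G03". Four terms are listed under it, all qualified NOS, for example "meningitis NOS".
- **Neurological:** "Diseases of the nervous system G00-G99".
- **Infectious Diseases:** "Certain infectious and parasitic diseases A00-B99".

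The neighbouring Encephalitis row is given as "Encephalitis, myelitis and encephalomyelitis G04".

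The Study One analysis text then says "Logistic regression will be used to estimate odds ratios for the risk for (specific) adverse events", comparing vaccine-exposed and unexposed groups. On counting, it says that "each person will only be counted once for each hospitalisation, the primary diagnosis", with repeat admissions and transfers for the same episode removed. No other part of the protocol assigns a further code to Meningitis.

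**The concern.** The label promises all meningitis, but the code delivers a remainder category. A code whose printed title is for other and unspecified causes is what is left once cases with a designated cause have been coded elsewhere.

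Two Study One products depend on the definition. The first is the background rate: the lead objective of Study One is to establish such rates for its key endpoints in women and infants. The second is the odds ratio for the specific event. If the row is reported as Meningitis, readers will compare its rate and odds ratio with other meningitis data, although only part of the disease has been counted.

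**Working it through.** No sample-size or power arithmetic applies, and the protocol states no expected meningitis figure to reproduce. The check sets the relevant parts of the protocol side by side.

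1. **What the row admits.** The single code is G03. Its printed title covers other and unspecified causes, and the four terms beneath are all NOS. The word other may let in some cases with a known cause, so the row is not purely the unexplained cases. It is still a residual category by its own title.

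2. **Where a cause-specific record can go.** If it carries another G code, it falls in Neurological, which takes the whole of G00-G99. If it carries an A or B code, it falls in Infectious Diseases, which takes the whole of A00-B99. In neither row can it be read as meningitis. The protocol does not list which individual codes in those ranges denote meningitis. The conclusion therefore rests on the printed title of G03 and on the absence of any other code in the row, not on a code book.

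3. **Whether a later rule repairs this.** The counting rule refers to the primary diagnosis and removes repeat admissions. Nothing in it moves a cause-specific record into the Meningitis row.

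4. **Overlap.** G03 lies inside G00-G99, so every Meningitis case also meets the Neurological definition. The protocol does not say whether such a case is shown in both rows or in one.

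5. **Direction of the effect.** Let *c* be the share of infant meningitis admissions coded to G03.
   - Rate reported = *c* × rate of all coded meningitis. This is too low whenever *c* < 1, that is, whenever at least one case is coded to a specified cause.
   - Events available to the odds ratio = *c* × all meningitis events. For a rare outcome, with *c* the same in both exposure groups, the standard error of the log odds ratio is larger by about 1/√*c*.

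6. **Size.** The protocol gives neither *c* nor any meningitis count or rate, so no numerical shortfall follows from it.

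**The case against.** The strongest reply is that nothing is lost. Cause-specific cases can still enter Study One through the Neurological or Infectious Diseases rows, and the table prints the code title beside the label, so a careful reader can see what is counted. The list is also introduced as what outcomes will include, which leaves it formally open, and Meningitis is one of eight infant rows and is not named as a primary endpoint.

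Much of this stands. The defect is misclassification between rows, not failure to capture, and it affects one outcome rather than Study One as a whole. But a whole-range row cannot yield a meningitis rate, and an open list does not change the definition actually given for this row.

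Three stronger readings are tempting, and the documents do not support them:

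- **That the undercount is several-fold.** Any such figure needs an assumed split between specified and unspecified causes, and the protocol offers none.
- **That the odds ratio would reflect diagnostic work-up rather than disease.** That bias requires the share coded to G03, or the vaccine effect, to differ in a way linked to exposure. Exposure does rise over calendar time, since funding began in 2012 within a 2009-2013 window, and year is not among the listed covariates. Even so, nothing in the protocol shows that coding or investigation changed over the period or differed by maternal vaccination.
- **That Encephalitis has the same fault.** The printed title of G04 has no residual wording, so the table does not show that cases are excluded from that row.

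**Conclusion.** The point holds as a mismatch between label and code. Followed as written, the plan counts only G03 records as infant Meningitis and leaves cause-specific meningitis inside two broad rows. The meningitis background rate would be too low, and the odds ratio would be less precise and would refer to a narrower outcome than its name. This direction requires only that some infant meningitis admissions in the period were coded to a specified cause. The magnitude is unknown from the documents, and bias in the odds ratio is not shown. It is worth correcting because a named outcome would be misreported and the correction is easy. It does not undermine the rest of Study One.

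**What to change.** Define Meningitis as G03 together with all cause-specific meningitis codes in G00-G99 and A00-B99, and list those codes individually. State that the row overlaps Neurological and Infectious Diseases, so that the rows are not summed or read as mutually exclusive. If the wider definition is not adopted, rename the row to match the title of G03 and do not report it as meningitis.

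The cost is an edit to the code list and a sentence on overlap. Both ranges are already Study One infant outcomes, so no new data source is needed, provided the extract keeps individual codes rather than only row-level flags. The change should be made before the analysis, which the protocol places in the second half of 2014, so that the outcome definition is not altered after results are seen.

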Note that in NZ, TdaP has been recommended in pregnant women between 20 and 36 weeks gestation since 2011 but had to be privately purchased. In October 2012, the MoH recommended and began fully funding TdaP nationally for pregnant women who were between 28 and 38 weeks gestation. There will be some variation, mainly prior to this date as some women will have received it both earlier and later than this in a range of regionally funded programmes. We are able to identify these exposures in the regionally funded programmes. We will not be able to identify private purchase. We know from anecdotal evidence that the number of women purchasing prior to funded programmes was very low but we cannot accurately quantify. GSK NZ have followed this up and confirm very few doses.

While TdaP was available via fee-for-service as early as 20 weeks gestation, a selection of DHBs began funding TdaP in pregnant women in 2012. Each DHB decided the gestation period required to receive funded TdaP. For example, Counties Manukau DHB-funded TdaP for women after 20 weeks gestation while Canterbury DHB funded TdaP for women between 30 and 36 weeks gestation. Again, these exposures can be identified.

Study participants

Hospitalisation data for the study period will be obtained from the National Minimum Dataset. Health outcomes in the study population that required contact with a hospital will be described for mothers by health outcome type and incidence per maternal age, ethnicity, deprivation, vaccination exposure and time interval from vaccination. For infants the health outcomes in the study population that required contact with a hospital will be described by infant ethnicity, age, deprivation, maternal age, ethnicity and deprivation and whether or not vaccination was given during pregnancy. The data for infants included in Study One will include the first year of life.

Vaccination status will be determined through the claims information submitted to the DHB and matched to the hospitalisation data. Notifications for pertussis will be determined from Environmental Science and Research (ESR) who provide disease surveillance to the government. ESR, under contract to the MoH, undertakes laboratory based surveillance of notifiable diseases and outbreak surveillance. Hospitalisations will be determined through the National Minimum Dataset. Hospitalisations and notifications will be matched to vaccine status using the National Health Index Number (NHI).

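### The Study One infant outcome labelled lower respiratory is coded as the whole respiratory range J00-J99, so upper respiratory admissions would count as lower respiratory events

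*Protocol*

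**What the plan says.** The Outcomes section of Study One introduces its table with "Hospitalisation outcomes of interest will include the following conditions". The left column names the outcome and the right column gives ICD codes. One infant row reads "Lower respiratory (bronchiolitis, asthma, pneumonia, acute unspecified LRTI, bronchiectasis, Acute bronchitis, lung abscesses/pyothorax", and the code entry beside it is "Diseases of the respiratory system J00-J99".

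Other rows of the same table are coded more finely. Meningitis is given as "Meningitis due to other and unspecified causes G03" and encephalitis as G04, while a separate neurological row takes all of G00-G99.

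The Analysis paragraph for Study One states: "Logistic regression will be used to estimate odds ratios for the risk for (specific) adverse events for both mothers and infants". It then says that "each person will only be counted once for each hospitalisation, the primary diagnosis and repeat admissions for the same episode will be removed". On follow-up, the Study participants section says: "The data for infants included in Study One will include the first year of life".

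The main Study One objective is to establish background rates for key endpoints in mothers and infants. The clinical hypothesis is that event rates after vaccination are similar to those without it.

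**The concern.** The label and the code rule of one row define two different outcomes. The label and its list cover lower respiratory disease only. The code range, by its own title, covers the respiratory system as a whole. Two analysts working from this row could build different endpoints and report both under the same name.

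Two results are at stake. The first is the background rate: any infant admitted only for upper respiratory illness would be added to a rate reported as lower respiratory. The second is the comparison of vaccinated and unvaccinated. Events that vaccination affects less than lower respiratory disease would move the odds ratio towards 1. In a study whose hypothesis is similarity, that movement favours the hypothesis and could mask a difference in either direction.

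**Working it through.** **Label against code.** The seven conditions in the row are all lower respiratory. The title of the code range contains no such limit. Three places could have narrowed it:

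- The table: no footnote or sub-code restricts this row. The meningitis and encephalitis rows beside the G00-G99 row show that the code column can separate a specific outcome from its chapter. The respiratory row does not do so.
- The Analysis paragraph: it refers to specific adverse events but does not say which J codes form one.
- The counting rule: it handles the primary diagnosis, repeat admissions and transfers. An upper respiratory primary diagnosis still falls within J00-J99.

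The mismatch therefore stands on the text alone. The protocol gives no rate, share or target effect for this outcome, so there is no stated figure to reproduce.

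**Illustrative size.** These inputs are assumptions, not taken from the documents:

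- u, the proportion of infants with any J00-J99 admission who had upper respiratory admissions alone: 10%, 20% or 40%.
- Risk of a lower respiratory admission in the unexposed, p: 3–10%.
- True lower respiratory odds ratio: 1.25 or 0.80.
- Upper-only admission equally likely in exposed and unexposed.

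*Background rate.* The reported rate is the lower respiratory rate divided by (1 − u), so the overstatement is 1/(1 − u) − 1:

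- u = 0.10: 1/0.90 − 1 = 11%
- u = 0.20: 1/0.80 − 1 = 25%
- u = 0.40: 1/0.60 − 1 = 67%

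*Odds ratio.* The upper-only risk is p·u/(1 − u), added to the lower respiratory risk in both groups. Worked example with p = 6%, u = 0.40 and true odds ratio 1.25:

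- Lower respiratory odds, unexposed: 0.06/0.94 = 0.0638. Exposed: 0.0638 × 1.25 = 0.0798, a risk of 0.0739.
- Upper-only risk: 0.06 × 0.40/0.60 = 0.04.
- J00-J99 risk: unexposed 0.1000, exposed 0.1139.
- Observed odds ratio: (0.1139/0.8861)/(0.1000/0.9000) = 1.16.

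Over p = 3–10%:

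| u | true 1.25 appears as | true 0.80 appears as |
|---|---|---|
| 10% | 1.23 | 0.82 |
| 20% | 1.20–1.21 | 0.84 |
| 40% | 1.15–1.16 | 0.87–0.88 |

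*Same effect on upper admissions.* If vaccination has the same odds ratio on upper-only admissions, the observed value over the same range is 1.25–1.28 for a true 1.25, and 0.79–0.80 for a true 0.80. There is then no pull towards 1.

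**The case against.** The strongest reply is that J00-J99 is a search range and the bracketed list is the outcome. Most infant rows pair a condition with a chapter or block (infectious diseases with A00-B99, congenital anomalies with Q00-Q99.9). Some rows also overlap: G03 and G04 lie inside G00-G99. A table of final, mutually exclusive endpoints would not look like this. The Analysis paragraph speaks of specific events, and code-level detail is often left to the analysis plan. This reading is possible, but the protocol does not state it. What the protocol does state is a code range that contradicts its own label, which is more than an omission.

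It is also fair to say that nothing is lost for good. J00-J99 contains the wanted conditions, and the narrower outcome can be derived from the same hospitalisation data. That makes the correction cheap but does not remove the need for it.

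A reader might infer three stronger things that the documents do not support:

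- *That dilution is certain.* It requires a smaller vaccine effect on upper than on lower admissions. No passage says so, and with equal effects it disappears.
- *That the size is known.* The upper respiratory share has no source in the protocol. A share of admissions is also not a share of infants: under the logistic model, an infant with both kinds of admission is one event under either definition. Using the admissions share would therefore overstate both effects for an infant-level outcome. The working defines u as infants with upper admissions alone for this reason.
- *That this row is the main proxy for pertussis.* Pertussis is captured directly, as a named condition in the infectious diseases row and through notifications matched to vaccine status. Lower respiratory admission is one outcome among several.

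**Conclusion.** The point holds in a limited form. The row contradicts itself, and no other part of the protocol resolves it. If the stated codes are applied, the lower respiratory background rate is too high whenever any infant has upper respiratory admissions alone; this needs no assumption about the vaccine. Movement of the odds ratio towards 1 is possible but conditional on a weaker vaccine effect on upper admissions.

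The figures in the working are illustrations. With 10–40% of J00-J99 infants having upper admissions alone, the rate is overstated by about 11–67%. With no effect on upper admissions, 1.25 would appear as about 1.23–1.15 and 0.80 as about 0.82–0.88. The true share could lie outside that range. The error should be corrected before analysis, but it affects one outcome row and does not undermine Study One as a whole.

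**What to change.** In the infant table, replace J00-J99 in the lower respiratory row with an explicit list of codes for the seven conditions already named there. Keep J00-J99 as a separate row, labelled as all respiratory admissions, and report it alongside. If the range was meant only as a search range, the protocol should say so and still give the codes that make up the endpoint.

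This needs no new data, since the hospitalisation extract already carries the diagnoses, and no planned result is dropped. The cost is a revised code list and somewhat fewer events, hence slightly less precision, in the specific outcome.
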